6.0 Treatment Plan

6.1 Study-Related Interventions

	Pre-Study ^a	O.R. Day (surgery)	Follow-up Post-Treatment Visits (+/- 2 weeks)			
			6 weeks	3 Mo	6 Mo	12 Mo
Informed consent	X					
Demographics	X					
Medical history	X		X	X	X	X
Concurrent meds	X	X	X	X	X	X
Height, Weight, BSA	X		X	X	X	X
Op Note, Path Report, Perfusion Flowsheet		X				
Adverse event evaluation		X ^d	X ^d			
Physical exam and ECOG PS	X		X	X	X	X
Vital signs	X	X	X	X	X	X
B-HCG ^c	X					
CBC w/diff, plts	X			X	X	X
CMP	X			X	X	X
CA-125	X			X	X	X
CT of Abdomen, pelvis ^b	X			X	X	X
FACT-O, FACT/GOG-NTX, and FACT/GOG-AD questionnaires	X		X	X	X	

a: Pre-Study visit will occur and pre-study procedures will be completed within 28 days prior to registration.

b: CT of abdomen/pelvis as per standard-of-care.

c: B-HCG is for women of child-bearing potential only.

d: Adverse event monitoring will begin at time of surgery and will continue for six (6) consecutive weeks. AEs will be recorded in WISER at the 6 week time point.

6.2 Treatment Administration

6.2.1 Surgical Intervention and Subsequent Chemotherapy

6.2.1.1 Preoperative Preparation

Patients will have a mechanical and antibiotic bowel preparation. Potential ostomy sites will be marked by the surgeon or the endostomal nurse prior to surgery.

6.2.1.2 HIPEC

Tumor Debulking and Establishment of Peritoneal Perfusion Circuit

The HIPEC will be preceded by a complete cytoreduction to maximize its therapeutic benefit. The goal of cytoreduction will be resection of all gross tumor. A generous midline incision will be utilized for all explorations. Resection of the peritoneum by stripping it off the abdominal wall combined with multi-visceral resections (such as splenectomy, large and small bowel resection, hysterectomy, etc.) will be utilized for maximal tumor debulking¹⁹.

Patients will be cooled to a core temperature of about 34 to 35° C by passive measures (i.e., not warming airway gases or intravenous solutions) during cytoreduction. After the completion of cytoreductive surgery, peritoneal perfusion catheters will be placed percutaneously. Two inflow catheters (22Fr) will be directed beneath the left and right hemidiaphragms. One or two outflow catheters (32Fr) will be placed in the pelvis. Intraperitoneal catheters will be placed as per institutional standard practice. Temperature probes will then be placed on the inflow and outflow catheters. The abdominal skin incision will be temporarily closed with a running suture to prevent leakage of peritoneal perfusate. A perfusion circuit will be established with 3 L of crystalloid perfusate solution, such as sodium chloride, Lactated Ringers or Plasmalyte. If a perfusion circuit cannot be established with 3 liters a 4th liter is acceptable, but under no circumstances should the volume of perfusate be greater than 4 liters. Flow rates should be at least one liter per minute. The pelvic catheters will drain to a reservoir containing a coarse filter for debris and to reduce foaming. The heated chemotherapy solution will be added and circulated through the institution's standard perfusion equipment. The temperature of the fluid in the patient-return and patient-directed tubing will be monitored using stainless steel couplers with temperature probe connectors and needle probes at the tips of one inflow and one outflow cannula. The abdomen will be gently massaged throughout the perfusion to improve drug distribution to all peritoneal surfaces. Constant temperature monitoring will be done at all temperature probes. A perfusion record will be completed during HIPEC (see Appendix E). Following the perfusion, the peritoneum will be washed out with 3 liters of the crystalloid perfusate.

HIPEC Chemotherapy Administration

A Phase II Trial Evaluating Quality of Life After HIPEC in Patients with Stage IIIC and IV Ovarian, Fallopian Tube or Primary Peritoneal Carcinoma
Wake Forest Baptist Comprehensive Cancer Center (WFBCCC)
CCCWFU 83216

Carboplatin will be added to the perfusate once outflow temperatures exceed 39°C at a dose of 800 mg/m²¹⁸. A maximum inflow temperature of 42.5°C is tolerated during the perfusion. The target outflow temperature is 40°C. The total perfusion time after the initial addition of carboplatin will be 90 minutes. The carboplatin dose will be calculated based on the body surface area noted on admission (or as close to surgery day as possible). Following the perfusion, the peritoneum will be washed out with 3 liters of perfusate and passively drained. The skin will then be opened, and the cannulas removed under direct vision. If a bowel resection is performed, any anastomoses may be completed before or after HIPEC; ostomies will be completed at the end of the entire procedure. The abdomen will be inspected and the required anastomoses will be created. The fascia and skin will then be closed in a standard fashion and the requisite ostomies will be created if necessary.

6.2.1.3 Postoperative Care

The patient will be transferred to the post-anesthesia care unit for aftercare and then to the intensive care unit, if needed. Early and late complications of surgery will be recorded in the patient's research chart.

6.3 General Concomitant Medication and Supportive Care Guidelines

Patients should receive *full supportive care*, including transfusions of blood and blood products, erythropoietin, neupogen, antibiotics, antiemetics, etc., as clinically indicated. Anti-inflammatory or narcotic analgesics may be offered as needed. Medications considered necessary for the patient's well-being may be given at the discretion of the investigator, i.e., chronic treatments for concomitant medical conditions, as well as agents required for life-threatening medical problems, etc. The reason(s) for treatment, dosage, and dates of treatment should be recorded on the flow sheets.

6.4 Duration of Therapy

Therapy (HIPEC) will be administered for 90 minutes with carboplatin 800 mg/m² during the surgery as described in Section 6.2.1.2 of this protocol.

6.5 Duration of Follow Up

Tumor assessment for all lesions will be performed while patients are in the protocol follow-up phase of this study at 3, 6, and 12 months. Patients who discontinue the trial without documented tumor progression should be evaluated for extent of disease at the time of trial discontinuation.

Patients will be followed for 30 days after the HIPEC intervention is administered for adverse events monitoring.

A Phase II Trial Evaluating Quality of Life After HIPEC in Patients with Stage IIIC and IV Ovarian, Fallopian Tube or Primary Peritoneal Carcinoma
Wake Forest Baptist Comprehensive Cancer Center (WFBCCC)
CCCWU 83216

Patients will be followed for a minimum of 30 days after removal from study or until death, whichever occurs first. Patients removed from study for unacceptable adverse events will be followed until resolution or stabilization of the adverse event.

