12.0 Data Management

The Appendices contain master copies of the case report forms (CRFs) to be used for this protocol.

Note: If the patient does not have protocol therapy at surgery, it is still necessary to submit Day 0 data and the No HIPEC Follow-Up form annually.

Informed consent document

EPIC

A Phase II Trial Evaluating Quality of Life After HIPEC in Patients with Stage IIIC and IV Ovarian, Fallopian Tube or Primary Peritoneal Carcinoma
Wake Forest Baptist Comprehensive Cancer Center (WFBCCC)
CCCWFU 83216

Protocol registration Form (Appendix B)	WISER
FACT-O, FACT-GOG-NTX4, FACT/GOG-AD (Appendices H, I, J)	WISER
Follow-up form (Appendix F)	WISER
RECIST measurement form (Appendix G)	WISER
Adverse Events Log (Appendix K)	WISER

The Protocol Registration Form and signed Informed Consent Form should be completed and faxed to the WFBCCC Registrar in order to enroll and randomize participants. All other CRFs & supporting documents should be faxed to the attention of the Study Coordinator according to the following schedule:

Form	Submission Schedule
Surgery Form	Form and reports within 30 days of surgery
Perfusion Record - HIPEC Form	Form within 30 days of surgery
Adverse Event Log	Form within 7 days of completion of time period.
Follow-Up / Measurement Form	Form and supporting documents within 7 days of mo. 3, 6, and 12
FACT-O, FACT/GOG-AD, FACT/GOG-NTX	Prestudy, , Week 6, months 3 and 6 post-treatment (follow-up)

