13.2 Analysis of Secondary Objective

13.2.1 To describe QOL in patients with advanced ovarian cancer treated with SOC NAC followed by CRS with HIPEC as determined by the FACT-O questionnaire at 3 and 6 months post-treatment, the distribution of QOL at 3 and 6 months post-treatment will be examined. The descriptive statistics of QOL at 3 and 6 months post-treatment will be presented. In addition, the longitudinal data of QOL over time will be displayed graphically with individual trajectories.

13.2.2. To describe neurotoxicity at the end of study, the descriptive statistics will be presented. Since neurotoxicity is a 4-item measure from FACT/GOG-NTX4, counts and percentages will be calculated. Mean and standard deviation will be also calculated.

A Phase II Trial Evaluating Quality of Life After HIPEC in Patients with Stage IIIC and IV Ovarian, Fallopian Tube or Primary Peritoneal Carcinoma
Wake Forest Baptist Comprehensive Cancer Center (WFBCCC)
CCCWFU 83216

13.2.3. To describe abdominal discomfort at the end of study, the descriptive statistics will be presented. The abdominal discomfort is a 4-item score from FACT-GOG/AD. Counts and percentages will be calculated. Mean and standard deviation will be also calculated.

13.2.4. The toxicities will be measured by the number and severity of adverse events defined by CTCAE v5.0. Counts and percentages will be calculated for each adverse event. Mean, standard deviation, median, and interquartile range will be calculated for number of adverse events.

13.2.5. The response rate using RECIST criteria at each time point will be estimated. Counts and percentages will be calculated.

13.2.6. This secondary objective is to estimate progression free survival using survival analysis. Survival will be measured up to the time until progression, date of last contact, or death, whichever comes first. Kaplan-Meier survival curves will be used to estimate the survival probabilities. The survival probabilities for the whole sample and for the stratified groups (weekly or 3-weekly) will be calculated. The log-rank test will be used to compare the two stratified groups.

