13.4 Estimated Accrual Rate

Accrual is expected to be 40 patients in 18 months. Targeted accrual should be met within 1 ½ years. Under the current amendment (Protocol Version Date: 03/14/2023), an additional 10 patients will be recruited at an accrual rate of 1 patient per month.

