Appendix F - FOLLOW-UP FORM

[contact]

Patient initials (Last, First): _____
Institution: _____

Page 1 of 1

Medical Record#: _____
Study number: **83216**

HIPEC

6 Week

3 month

†

6 month

12 month (PROs not filled out at this visit)

Please check visit and complete the rest of this form according to that protocol visit

Physical Exam/ vital signs DATE: ____/____/____ **(ECOG) Performance status** _____

Was the FACT – O Questionnaire completed? Yes _____ No _____ N/A _____

DATE: ____/____/____

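### PFS data collection stops at month 12 but the analysis runs to last contact: later progressions are not systematically captured, and the median may be out of reach if it exceeds about 12 months

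*Combined protocol and SAP*

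**What the plan says.** Objective 2.2.6 is to estimate PFS in patients treated with neoadjuvant chemotherapy followed by surgery with HIPEC. Outcome 5.2.6 names PFS without a time horizon, whereas 5.2.4 (toxicity) and 5.2.5 (response) each have one.

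Data collection for HIPEC patients ends at month 12 in four places:
- the visit table in 6.1 has no column after 12 months;
- 6.5 places tumour assessment "while patients are in the protocol follow-up phase of this study at 3, 6, and 12 months";
- the last visit on the follow-up form (Appendix F) is "12 month (PROs not filled out at this visit";
- the submission schedule in 12.0 for the follow-up and measurement forms reads "Form and supporting documents within 7 days of mo. 3, 6, and 12".

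The analysis text in 13.2.6 has no such limit: "Survival will be measured up to the time until progression, date of last contact, or death, whichever comes first". It adds that "Kaplan-Meier survival curves will be used to estimate the survival probabilities", and plans a log-rank test between weekly and 3-weekly groups. It names neither a median nor a PFS probability at a fixed time.

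On timing, 13.4 says "Accrual is expected to be 40 patients in 18 months" and that, under the amendment, "an additional 10 patients will be recruited at an accrual rate of 1 patient per month". Section 13.5 gives a total length of about 3 years, and about 2 years for the amendment.

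**The concern.** The collection rule and the analysis rule do not meet. There are two ways to run the plan as written, and it does not choose between them.

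If PFS information in practice ends with the month-12 form, patients enrolled early are event-free or not at one year and nothing more is learned, although many could have been observed for two years or longer. Events are lost to the Kaplan-Meier curve and to the log-rank test, and the curve may stop before it reaches 50%.

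If instead patients are carried to last contact, no scheduled scan or form supports the time after month 12. A patient seen or telephoned at month 20 without imaging would count as progression-free to month 20, which pushes the curve upward.

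**Working it through.** **The plan's own figure.** There is none for PFS: no median, rate, event count or precision. The only sample-size figure, the detectable FACT-O difference in 13.3, reproduces. A one-sample t-test with SD 19.2, two-sided 20% level and 80% power gives 5.87 at n = 49 and 6.13 at n = 45, against the stated 5.9 and 6.1. It says nothing about PFS.

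**Inputs from the documents.** N = 50 (13.3); 40 patients in 18 months, then 10 at one per month (13.4); about 3 years in total (13.5); last scheduled assessment at month 12 (6.5).

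**Assumptions, not in the documents.** The 10 added patients follow directly on the first 40. Entry is taken as the start of PFS time. PFS is exponential with median m, shown over a range. There is no loss to follow-up.

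**Step 1: potential follow-up.** Entries are spread evenly over months 0–18 for the 40 (mean 9) and fall at months 19 to 28 for the 10 (mean 23.5).
- Closure at the last patient's month 12, i.e. 28 + 12 = month 40: (40 × 31 + 10 × 16.5)/50 = 28.1 months.
- Closure at the stated 3 years, month 36: (40 × 27 + 10 × 12.5)/50 = 24.1 months. The last four patients, entered at months 25–28, would then have less than 12 months.

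**Step 2: events lost by stopping at month 12.** Expected events are the sum over patients of 1 − 2^(−f/m), where f is potential follow-up, first uncapped and then capped at 12. The share lost is 1 − capped/uncapped. For m = 12 and closure at month 40: capped 50 × 0.5 = 25.0, uncapped 39.1, lost 1 − 25.0/39.1 = 36%.

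**Step 3: chance the curve reaches 50% by month 12.** With all 50 observed to month 12, this is P(Binomial(50, 1 − 2^(−12/m)) ≥ 25).

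| True median (months) | Events by month 12 / by month 40 | Lost, closure month 40 | Lost, closure month 36 | Chance median reached by month 12 |
|---|---|---|---|---|
| 6 | 37.5 / 47.1 | 20% | 18% | >99% |
| 8 | 32.3 / 44.5 | 27% | 24% | 99% |
| 10 | 28.2 / 41.8 | 32% | 29% | 86% |
| 12 | 25.0 / 39.1 | 36% | 32% | 56% |
| 15 | 21.3 / 35.5 | 40% | 35% | 18% |
| 18 | 18.5 / 32.3 | 43% | 38% | 4% |

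The last column falls to 50% at a true median of about 12.4 months.

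**The case against.** The study calls itself descriptive, its primary endpoint is 6-week quality of life, and a 12-month horizon looks deliberate: 18 + 12 = 30 months fits the 3 years, and 10 + 12 = 22 months fits the amendment's 2 years. The plan promises Kaplan-Meier probabilities, not a median, and the 3-, 6- and 12-month probabilities can be estimated from the scheduled visits. All of that stands. It limits the point to an improvement, but it does not settle which end of follow-up 13.2.6 intends.

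A reader might infer several stronger things that the documents do not support:
- *That every event-free patient is censored at month 12.* Section 13.2.6 uses last contact and sets no cut-off. The gap is in scheduled assessments and forms.
- *That the median will probably not be estimable, or that a third or more of events are lost.* Both depend on a true median that the plan never gives. The first needs more than about 12.4 months. The second needs at least about 10.4 months with closure at month 40, or about 13 with closure at 3 years.
- *That untreated patients are followed longer than treated ones.* For patients without protocol therapy at surgery, 12.0 says "it is still necessary to submit Day 0 data and the No HIPEC Follow-Up form annually", but gives no duration. A single annual form would fall at month 12.

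**Conclusion.** The point holds as a mismatch between collection and analysis. Scheduled PFS data for HIPEC patients end at month 12, while 13.2.6 runs to last contact. Later progressions are not systematically captured, and censoring at last contact could count unassessed time as progression-free.

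The size is conditional. Under exponential PFS and contiguous accrual, stopping at month 12 forgoes roughly a fifth of obtainable events if the median is 6 months and about two-fifths if it is 18. The median may not be estimable if it exceeds about 12 months, and is likely to be reached if it is 10 or less. Twelve-month PFS stays estimable either way.

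The 24 to 28 months of mean potential follow-up is derived, not stated in the plan. The documents do not say when the added accrual starts relative to the first 40, and a long gap before it would lengthen follow-up and raise the losses. This is a cheap improvement to a secondary objective and does not affect the primary analysis.

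**What to change.** Keep the visits as they are. In 6.5 and 13.2.6, state that:
- at study closure, the date of first documented progression, death or last progression-free assessment is abstracted from routine records for every HIPEC patient;
- event-free patients are censored at the last progression-free assessment, not at last contact;
- Kaplan-Meier is run to that common closure date;
- 12-month PFS is reported with a 95% confidence interval, plus the median if reached.

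The closure date should be named, for example the last patient's month-12 visit.

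Cost: one chart abstraction for about 50 patients and possibly a consent or IRB amendment. No study visit or scan is added. The downside is that progression dates after month 12 rest on routine scan intervals, and the documents do not guarantee that such scans exist. That part of the curve should be labelled accordingly.

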6.6 Criteria for Removal from Study

Patients may withdraw/be withdrawn from the trial at any time and for any reason. Patients will not be replaced. Some possible reasons for early withdrawal include the following:

- Development of an intercurrent medical condition or need for concomitant treatment that precludes further participation in the trial
- Unacceptable toxicity or any adverse event that precludes further participation in the trial
- Study completion or discontinuation
- Patient withdraws consent to continued participation in the trial

The reason and date of discontinuation are to be documented in the patient's medical record and in the CRF.

The investigator should complete all end of treatment procedures when a patient withdraws from treatment. All patients who discontinue the trial secondary to an adverse event should be followed until resolution, stabilization or return to a baseline condition. All patients who undergo HIPEC with study agents will be included in any safety analysis.

The Co-Principal Investigators may discontinue the trial at any time. Reasons for early trial discontinuation may include, but are not limited to, unacceptable toxicity of study treatment, a request to discontinue the trial from a regulatory authority or an IRB, or poor enrollment.

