1.3 HIPEC

Hyperthermic intraperitoneal chemotherapy (HIPEC) is based on the rationale that intraperitoneal chemotherapy has a substantial pharmacokinetic advantage over systemic chemotherapy. The hyperthermia effects cell membranes, cytoskeletons, synthesis of macromolecules and DNA repair mechanisms.³⁻⁴ Furthermore, mild hyperthermia has been shown to potentiate the anti-tumor effects of oxaliplatin, mitomycin C (MMC), and cisplatin.⁵⁻⁹ While hyperthermia has some cytostatic properties, it is the synergistic effect on chemotherapeutic agents which has lead most centers to utilize hyperthermia with chemoperfusion. The primary objective of HIPEC is to maximize drug-tumor interaction while minimizing systemic toxicity. The HIPEC is delivered at the time of CRS and is a single treatment. This single dose treatment offers significant advantages over conventional IP chemotherapy in the decrease in the number of cycles/treatment time and recovery time after each IP dose are avoided.

The timing of peritoneal perfusion is critically important. Extensive evidence shows that the effect of postoperative versus intraoperative peritoneal perfusion is reduced by the rapid formation of intra-abdominal adhesions as well as complications related to intra-abdominal catheters.⁹⁻¹¹ Intraoperative peritoneal perfusion not only allows for the instillation of chemotherapeutic agents in an adhesion-free environment, it also minimizes the number of viable exfoliated tumor cells after resection.¹²⁻¹⁴ Taken together, this represents the biologic foundation for the current use of HIPEC in the treatment of advanced ovarian malignancies.

A Phase II Trial Evaluating Quality of Life After HIPEC in Patients with Stage IIIC and IV Ovarian, Fallopian Tube or Primary Peritoneal Carcinoma
Wake Forest Baptist Comprehensive Cancer Center (WFBCCC)
CCCWFU 83216

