5.0 Study Outcomes and Study Measures

5.1 Primary Outcome

- 5.1.1 QOL in patients with advanced ovarian cancer treated with SOC NAC followed by CRS with HIPEC as determined by the FACT-O questionnaire at 6 weeks post-treatment

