13.0 Statistical Considerations

13.1 Analysis of Primary Objective

This is a descriptive study. The primary objective is to compare the QOL in patients with advanced ovarian cancer treated with SOC NAC followed by CRS with HIPEC vs. QOL in patients treated with IV chemotherapy at 6 weeks post-treatment presented in Armstrong et al. (2006). Only the patients treated with SOC NAC followed by CRS with HIPEC will be recruited in this study. The summary data of QOL for patients treated with IV chemotherapy collected in Armstrong et al. (2006) will be directly used. The same as Armstrong et al., QOL will be measured using the Fact-O questionnaire and treatment as a continuous outcome. The distribution of QOL at 6 weeks post-treatment will be examined. The descriptive statistics such as mean, standard deviation, median and interquartile range will be calculated. One sample t-test will be used to compare the mean QOL in the study sample to the mean QOL based on Armstrong et al.

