13.3 Power and Sample Size

The power calculation is performed to test the primary objective. It is calculated to compare the mean QOL between the study patients and the mean QOL from Armstrong et al. (2006). Based on Armstrong et al., the standard deviation of QOL at 6 weeks post treatment is 19.2. Fifty patients will be recruited. The dropout rate is anticipated to be very small, around 1 to 2% at 6 weeks post treatment. Assuming 80% power, a two-sided test and a significance level of 20%, the minimal detectable difference of QOL between the study sample and Armstrong et al. is 5.9. If assuming a higher dropout rate, say 10% at 6 weeks post treatment, the minimal detectable difference for QOL is 6.1. Based on Armstrong et al., the mean difference of QOL between the two standard treatments (IV vs. intraperitoneal) is 5.2. We assume that the mean difference between HIPEC and IV can be larger. However, we are also aware that we may not have enough power to detect the difference. This study is for the descriptive purpose. The data collected in this study can be very useful for future research.

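### Section 6.6 allows removal from the trial after a one-off treatment and no section requires a FACT-O after removal, so the 6-week mean can be biased upward

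*Combined protocol and SAP*

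**What the plan says.** **Treatment.** Section 1.3 states: "The HIPEC is delivered at the time of CRS and is a single treatment". Section 6.4 sets the perfusion at 90 minutes during surgery. After the operating-room day, the 6.1 schedule holds only visits, labs, CT, adverse-event recording and questionnaires.

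**Endpoint and test.** The primary outcome (5.1) is quality of life "as determined by the FACT-O questionnaire at 6 weeks post-treatment". Section 13.1 says: "One sample t-test will be used to compare the mean QOL in the study sample" with a fixed mean taken from an earlier randomised trial.

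**Removal.** Section 6.6 permits withdrawal from the trial at any point and on any ground, without replacement. Its examples include "Unacceptable toxicity or any adverse event that precludes further participation in the trial". They also include an intercurrent condition, or a need for concomitant treatment, with the same qualifier that it must rule out continued participation.

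**After removal.** Four provisions apply:
- Section 6.5: "Patients will be followed for a minimum of 30 days after removal from study or until death, whichever occurs first".
- Sections 6.5 and 6.6: adverse events leading to removal are followed until they resolve or stabilise.
- Section 6.5: a patient leaving without documented progression should have the extent of disease evaluated at that time.
- Section 6.6: "The investigator should complete all end of treatment procedures when a patient withdraws from treatment".

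None of these names FACT-O, NTX or AD.

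**Analysis.** Section 6.6 guarantees inclusion of every HIPEC patient for safety analyses only. Section 13.1 defines no quality-of-life analysis set and no rule for a missing score or for death before 6 weeks. Section 13.3 treats dropout purely as lost sample size: "The dropout rate is anticipated to be very small, around 1 to 2% at 6 weeks post treatment", with 10% as a sensitivity case.

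**The concern.** Removal rules of this kind suit repeated dosing, where stopping treatment and leaving the study are different events. Here no study treatment remains after perfusion, so removal can only end observation. Section 7.3 speaks of removal from study therapy, but 6.6 never draws that line. The instruction about withdrawing from treatment has nothing to act on once perfusion is over, and the 6.1 schedule has no column for the procedures it invokes.

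The grounds for removal are plausibly tied to the endpoint: a patient with a serious complication is likely to report poor quality of life. The t-test uses only patients with a score, and with no concurrent arm such losses have nothing to cancel against. If the missing patients would have scored low, HIPEC looks better tolerated than it was.

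Removal also costs the later FACT-O, NTX and AD assessments. Because 13.2.6 ends PFS follow-up at last contact, it may also censor PFS informatively.

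**Working it through.** **Inputs.** From 13.3: SD 19.2, N = 50, two-sided significance level 20%, power 80%, dropout 1 to 2% or 10%, detectable difference 5.9 or 6.1, and a reference difference of 5.2 between IV and intraperitoneal treatment. Two assumptions are added: normally distributed scores, and higher FACT-O meaning better quality of life (the documents give no scoring key).

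**Step 1. Reproduce the plan's figures.** For a one-sample t-test by the noncentral t distribution:
- n = 50 × 0.98 = 49 gives 5.87, which rounds to the stated 5.9.
- n = 50 × 0.90 = 45 gives 6.13, which rounds to the stated 6.1.

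The normal approximation (1.282 + 0.842) × 19.2 / √n gives 5.82 and 6.08. Both stated figures hold.

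**Step 2. Worst-case bias.** If the lowest-scoring fraction d is missing, the completers' mean exceeds the full mean on average by SD × φ(z_d) / (1 − d), where z_d is the d-quantile of the standard normal.
- d = 0.02: 19.2 × 0.0484 / 0.98 = 0.95.
- d = 0.10: 19.2 × 0.1755 / 0.90 = 3.74.

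**Step 3. Bias for an assumed gap.** If completers average g points more than leavers would have, the bias is d × g. The documents give no leaver scores, so g is shown from 10 to 30 points.

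| Dropout by 6 weeks | Expected missing of 50 | Worst case | g = 10 | g = 30 |
|---|---|---|---|---|
| 1% | 0.5 | 0.52 | 0.1 | 0.3 |
| 2% | 1 | 0.95 | 0.2 | 0.6 |
| 5% | 2.5 | 2.08 | 0.5 | 1.5 |
| 10% | 5 | 3.74 | 1.0 | 3.0 |

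**Step 4. Compare with the plan's yardsticks.**
- At 2%, the worst case is 0.95 / 5.9 = 16% of the detectable difference.
- At 10%, it is 3.74 / 6.1 = 61% of the detectable difference and 3.74 / 5.2 = 72% of the reference difference.
- Section 13.3 shows 10% dropout costing 6.1 − 5.9 = 0.2 points of detectable difference. The possible bias at that dropout, 1.0 to 3.74 points, is not mentioned.

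**Step 5. Effect on the test.** If the true mean equals the external mean, the chance of a significant result favouring HIPEC should be 10% (half of 20%). With the SD held at 19.2, the chance becomes:
- at 2% dropout, at most about 17%;
- at 10% dropout, about 18% to 40% for gaps of 10 to 30 points, and about 51% in the worst case.

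**The case against.** **The text is permissive, not directive.** The grounds in 6.6 are possible reasons, and the clinical ones apply only where they rule out further participation. Since participation after surgery means visits, questionnaires, labs and scans, a strict reading would remove few patients. Section 6.3 also allows supportive care and necessary medication on study, so new treatment alone is not a ground for removal. This stands as a limit on how often removal should occur. It does not close the gap, because the qualifier is undefined and no questionnaire is required once removal happens.

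**Follow-up is long enough.** A reader might infer that the 30-day clause lets follow-up lapse before the 6-week assessment. The documents do not support that. The 6.1 schedule gives post-treatment visits a window of plus or minus 2 weeks, so the 6-week visit opens at about day 42 − 14 = 28. Removal on the day of surgery still gives follow-up to day 30, and adverse events leading to removal are followed to resolution or stabilisation. The gap is the missing questionnaire, not the length of contact.

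**Planned dropout is small.** At 1 to 2%, even the worst case stays below 1 point. This stands. The larger figures depend on reaching the protocol's own 10% case.

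**PFS has a partial safeguard.** The extent-of-disease evaluation at discontinuation captures status at that moment. It does not capture later progression.

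**The study calls itself descriptive** and admits that power may be insufficient. That lowers the stakes of the test, but a descriptive mean is biased by the same mechanism.

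**Conclusion.** The plan allows removal from the trial on health grounds after its only treatment has been given, and does not require the primary questionnaire afterwards. The 6-week mean can therefore be biased upward. Under the normal model the size is at most about 0.95 points at the planned 2% dropout and up to about 3.7 points at 10%. With assumed gaps of 10 to 30 points, it is 0.2 to 0.6 and 1.0 to 3.0 points.

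A reader might infer that the mean will be biased in HIPEC's favour. The documents do not establish this. It requires that removals occur before the assessment and that those removed would have scored lower, and the documents show neither. The effect on the comparison also depends on attrition behind the external mean, which they do not report.

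This is a worthwhile, inexpensive correction to the plan, not a flaw that invalidates it.

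**What to change.** **Sections 6.5 and 6.6.**
- Separate the end of treatment from the end of data collection.
- State that an adverse event, intercurrent illness or new treatment after perfusion does not by itself end scheduled data collection.
- Continue FACT-O, NTX and AD at 6 weeks, 3 and 6 months, and the 3-, 6- and 12-month assessments, as in 6.1, unless the patient withdraws consent, is lost or dies.
- Replace the undefined end-of-treatment procedures with a FACT-O, NTX and AD requested at withdrawal.
- State that the 30-day clause does not replace the 6.1 visits.

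**Section 13.1.** Report the number of patients without a 6-week score by reason, including death. Add a simple sensitivity analysis, for example recomputing the mean with missing scores set 10 to 30 points below the completers' mean.

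**Cost.** Amendment wording, a few questionnaires, and some extra contact effort for unwell patients. Clinical management does not change. A 6-week score that is not collected on time cannot be recovered later.
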